4. LIST OF ACRONYMS/ABBREVIATIONS

AE	Adverse event
ANOVA	Analysis of variance
ASA	American Society of Anesthesiologists
AUC	Area Under the Curve
BMI	Body mass index
C _{max}	Maximum plasma concentration
CFR	Code of Federal Regulations
CL/F	Apparent clearance
CRF	Case report form
d	Day
eCRF	Electronic case report form
ED	Emergency Department
FDA	Food and Drug Administration
GCP	Good Clinical Practice
HCl	Hydrochloride
h	Hour(s)
ICF	Informed consent form
ICH	International Council for Harmonisation
IEC	Independent Ethics Committee
IPO	International Pain Outcome
IRB	Institutional Review Board
IV	Intravenous
MedDRA	Medical Dictionary for Regulatory Activities
NRS	Numeric rating scale
NSAIDs	Nonsteroidal anti-inflammatory drugs
OMED	Oral morphine equivalent
OR	Operating room
PACU	Post-anesthesia care unit
PCS	Pain catastrophizing scale
PD	Pharmacodynamic
PK	Pharmacokinetic
PO	Oral
POD	Post-operative day
PRN	As needed
PTAE	Pretreatment Adverse Event
SAE	Serious adverse event
SAP	Statistical analysis plan
SD	Standard Deviation
t _{1/2el}	Apparent terminal elimination half-life
T _{max}	Time to maximum plasma concentration

TEAE	Treatment-emergent adverse event
US	United States
Vd	Apparent volume of distribution

5. ETHICS

5.1. Institutional Review Board/Independent Ethics Committee

Prior to enrolling subjects into this study, each study site will obtain the approval of an Institutional Review Board (IRB)/Independent Ethics Committee (IEC) that complies with the International Council for Harmonisation (ICH) Good Clinical Practice (GCP) and/or the United States (US) Food and Drug Administration (FDA) Title 21 Code of Federal Regulations (CFR) Part 56. Attention is directed to the basic elements that are required to be incorporated into the informed consent form (ICF) under 21 CFR Part 50.25 and ICH GCP.

5.2. Ethical Conduct of the Study

This study will be conducted in accordance with the clinical research guidelines established by the FDA Title 21 CFR, Parts 50, 54, 56, and 312, and the ICH GCP. Study documents will be maintained in accordance with applicable regulations.

5.3. Subject Information and Consent

Before a subject undergoes any study-specific screening procedures, the investigator or designee will thoroughly explain to the subject the purpose of the study, the associated procedures, and any expected effects and potential adverse reactions. A copy of the IRB-approved ICF will be provided to the subject, who will be given sufficient time and opportunity to inquire about the details of the study and decide whether or not to participate. The subject, and the study staff with whom he or she discusses the ICF, will sign and date the ICF. A photocopy of the signed ICF will be given to the subject.

The investigator will explain to the subject that he or she is completely free to decline entry into the study and may withdraw from the study at any time, for any reason, without risking his or her medical care. Similarly, the investigator and/or Pacira Pharmaceuticals, Inc. (“Pacira”) will be free to withdraw the subject at any time for safety or administrative reasons. Any other requirements necessary for the protection of the human rights of the subject will also be explained, according to the current ICH GCP (E6) and the Declaration of Helsinki (1964, and as amended through 2000 [Edinburgh]).

6. INVESTIGATORS AND STUDY ADMINISTRATION STRUCTURE

Information regarding the investigators, study sites, and other service providers is available upon request to the IRB/IECs and regulatory agencies.

7. INTRODUCTION

7.1. Indication

EXPAREL® was developed to extend pain relief with a single-dose administration without the use of indwelling catheters and to decrease the requirement for supplemental opioid medications.

EXPAREL is indicated for single-dose infiltration in adults to produce postsurgical local analgesia and as an interscalene brachial plexus nerve block to produce postsurgical regional analgesia.

Effective postsurgical pain control is a critical element in subject recovery following surgery, as the majority of subjects may experience significant pain, particularly in the first few days. Improved postsurgical pain management contributes to better healing, faster subject mobilization, shortened hospital stays, and reduced healthcare costs ([American Society of Anesthesiologists Task Force on Pain Management 1995](#)).

7.2. Current Therapies/Treatments

Current modalities of postsurgical analgesia include wound infiltration with local anesthetics combined with the systemic administration of analgesics (multimodal therapy). Multimodal therapy usually includes opioid medications, which have considerable drawbacks, including time and resources required for monitoring opioid-related side effects. A reduction in the use of postsurgical opioids is desirable to decrease the incidence and severity of opioid induced adverse events (AEs), such as respiratory depression, nausea, vomiting, constipation, somnolence, pruritus, and urinary retention.

With over 70 million surgeries performed annually in the US, postsurgical pain is a ubiquitous condition among the US population. While it is a predictable component of the postsurgical process, such pain is often poorly managed, resulting in clinical and physiological changes that increase morbidity and mortality (inability to ambulate early, etc.), diminish quality of life, and extend length of stay, thereby increasing hospital expenditures ([Oderda 2007](#)) and reducing subject satisfaction. Effective relief of acute pain with minimal opioid complications, on the other hand, may improve clinical outcomes, avoid complications (like delay in regaining bowel function or an inability to tolerate liquid and solid oral [PO] intake, etc.), and conserve healthcare resources. As such, the Joint Commission on Accreditation of Healthcare Organizations requires that all healthcare facilities practice adequate pain management and monitor opioid-related AEs ([Apfelbaum 2003](#)).

Opioid analgesics have long been established to be the most effective agents used for the management of moderate to severe postsurgical pain and are currently considered the mainstay of treatment. Opioid-only regimens are common and intravenous (IV) subject-controlled analgesia is a widely used delivery system for morphine sulfate. However, AEs related to opioid administration (e.g., nausea, vomiting, ileus, confusion) represent one important reason that there is a need to develop opioid-sparing strategies. Indeed, fear of gastrointestinal AEs, such as nausea and vomiting, as well as respiratory depression, present major limitations for the widespread use of opioid analgesics ([Chernin 2001](#), [Viscusi 2009](#)). Furthermore, management of opioid-related AEs often requires medical attention (e.g., opioid antagonists, antiemetic agents) and increased pharmacy/nursing time, which may raise healthcare expenses ([Carroll 1994](#)).

7.3. EXPAREL (Bupivacaine Liposome Injectable Suspension)

Bupivacaine is one of the longer-acting local anesthetics, but even so it has a limited duration of action after local administration, usually less than 8 hours. EXPAREL (Pacira Pharmaceuticals, Inc., ["Pacira"]) is a bupivacaine liposome injectable suspension. It consists of microscopic spherical, multivesicular liposomes (DepoFoam® drug delivery system) organized in a honeycomb-like structure comprising numerous non-concentric internal aqueous chambers containing a bupivacaine base at a concentration of 13.3 mg/mL. Each chamber is separated from adjacent chambers by lipid membranes. The lipids (phospholipids, cholesterol, and triglycerides) are naturally occurring or close analogs of endogenous lipids. Bupivacaine is slowly released from the DepoFoam particles by a complex mechanism involving reorganization of the barrier lipid membranes and subsequent diffusion of the drug over an extended period of time.

EXPAREL was approved by the US FDA in 2011 for administration into the surgical site to produce postsurgical analgesia. The active ingredient (bupivacaine) and inactive ingredient (DepoFoam) of EXPAREL are each contained, though separately, in FDA-approved products.

- Bupivacaine hydrochloride (HCl) solution, a well-characterized anesthetic/analgesic, with more than 35 years of use in the US.
- DepoFoam, a liposomal extended-release formulation contained in the marketed product DepoCyt® (1999). The form of DepoFoam used in EXPAREL has a slightly different mixture of liquid components than that used in DepoCyt.

7.4. Summary of Human Experience with EXPAREL

Pacira has conducted more than 36 clinical studies and one observational follow-up study to investigate EXPAREL. Across these studies, over 1800 human subjects received EXPAREL at doses ranging from 2 mg to 665 mg (equivalent to 2 mg to 750 mg bupivacaine HCl) administered by various routes: local infiltration into the surgical site, subcutaneous, perineural (or nerve block), and epidural. EXPAREL has been generally well tolerated and, in active comparator studies, AEs occurred at a similar rate as the corresponding bupivacaine HCl controls.

EXPAREL was initially approved by the US FDA in 2011 for single-dose administration into the surgical site to produce postsurgical analgesia. The indication was amended and approved by the US FDA in 2018 to read: "EXPAREL is indicated for single-dose infiltration in adults to produce postsurgical local analgesia and as an interscalene brachial plexus block to produce postsurgical regional analgesia." Since its approval, EXPAREL has been administered to approximately 5 million subjects in the US (January 2019).

Following the initial approval of EXPAREL, numerous clinical studies were conducted in which EXPAREL was administered via various routes of administration, including interscalene nerve block (Sternlicht 2014, Feierman 2014).

Please see the [EXPAREL Full Prescribing Information](#) (November 2018) for complete safety information regarding EXPAREL (liposome bupivacaine injectable suspension): <https://www.exparel.com/hcp/prescriptioninformation.pdf>.

7.5. Rationale for the Study

Pacira is investigating the pharmacokinetics (PK), efficacy, and safety of EXPAREL administered as combined sciatic (in the popliteal fossa) and saphenous (in the adductor canal) nerve block in healthy adult subjects undergoing lower extremity surgeries.

A dose of 20 mL (266 mg) EXPAREL with 20 mL of saline or EXPAREL admixed with 20 mL (50 mg) 0.25% bupivacaine HCl is expected to provide prolonged pain relief after these painful procedures compared with 40 mL (100mg) 0.25% bupivacaine HCl when injected in 20 mL volumes in sciatic nerve (in the popliteal fossa) and the saphenous nerve (in the adductor canal).

8. OBJECTIVES

The study objectives following the administration of study drug as a combined sciatic (in the popliteal fossa) and saphenous (in the adductor canal) nerve blocks in subjects undergoing lower extremity surgeries are listed below.

8.1. Primary Objective

To compare the magnitude of the analgesic effect following a single dose injection of EXPAREL vs. 0.25% bupivacaine HCl.

8.2. Secondary Objectives

- To compare the total opioid consumption (in oral morphine equivalents) from 0 to 96 hours following a single dose injection of EXPAREL vs. 0.25% bupivacaine HCl
- To compare the time to first opioid consumption following a single dose injection of EXPAREL vs. 0.25% bupivacaine HCl
- To characterize and compare the magnitude of the analgesic effect following a single dose injection of EXPAREL vs. EXPAREL admixed with 0.25% bupivacaine HCl
- To characterize and compare the magnitude of the duration of motor block following a single dose injection of EXPAREL vs. EXPAREL admixed with 0.25% bupivacaine HCl
- To assess the efficacy, safety, and pharmacokinetic (PK) profile of EXPAREL; EXPAREL admixed with 0.25% bupivacaine HCl and/or 0.25% bupivacaine HCl

9. OVERALL STUDY DESIGN AND PLAN

9.1. Study Design

This is a Phase 3, multicenter, randomized, double-blind, active controlled, 3-arm study in approximately 120 subjects undergoing lower extremity surgeries. The study will have 2 cohorts. Both cohorts will enroll in parallel.

[figure not shown]
Cohort 1 will enroll about 60 subjects undergoing bunionectomy to obtain information on PK profile, pharmacodynamics (PD), efficacy, and safety. Subjects in this cohort will be randomized (1:1:1) to receive combined sciatic (in the popliteal fossa) and saphenous (in the adductor canal) nerve blocks with EXPAREL, EXPAREL admixed with 0.25% bupivacaine HCl, or 0.25% bupivacaine HCl. Only select sites will enroll subjects for Cohort 1.

Cohort 2 will enroll about 60 subjects to obtain information on efficacy and safety. Subjects in this cohort will receive combined sciatic (in the popliteal fossa) and saphenous (in the adductor canal) nerve blocks. Subjects will be randomized (1:1:1) to receive EXPAREL, EXPAREL admixed with 0.25% bupivacaine HCl, or 0.25% bupivacaine HCl, and will be stratified by each surgery grouping.

Subjects in Cohort 1 and Cohort 2 will be discharged after the completion of the 168 h and 96 h assessments, respectively.

An adaptive study design will be used in this study. For efficacy, an interim analysis will occur when a total of approximately 60 subjects combined from either Cohort 1 or Cohort 2 have enrolled and provided complete assessment data for their primary efficacy outcome.

Figure 1: Study Schema

Note: Cohort 1 will enroll bunionectomy subjects only.

9.2. Duration of the Study and Subject Participation

Participation will begin upon signing of the ICF. No more than 30 days should pass between signing the ICF and study drug administration. Study drug administration will be on the same day of surgery. A follow-up phone call will occur on Post-operative Day (POD) 14 (± 3 days). Therefore, each subject may participate in the study for up to a maximum of 47 days.

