12.4. Safety Endpoints

- Incidence of treatment-emergent AEs and SAEs from the start of block procedure through POD 14

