13.11. Postsurgical Day 14 Phone Call

- Remind subject to complete and return the e-diary, if applicable, after POD 14 assessment.
- Ask the subject about any new AE(s) and the resolution of any ongoing adverse event(s) since discharge. Record any adverse event information.
- Ask the subject about any medication(s) taken, that were not reported in the e-diary, since discharge from the health care facility.

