14.1.2. Recording Adverse Events

It is the responsibility of the Investigator to document all AEs (i.e., PTAEs and TEAEs) with an onset after the subject signs the ICF. For the purpose of this study, all AEs that occur through POD 14 must be recorded regardless of whether or not they are considered related to study drug. Any AEs occurring after POD 14 only need to be reported if considered related to study drug by investigator. Whenever feasible, AE terms must be documented as medical diagnoses (highest possible level of integration); otherwise, the AEs must be reported separately as individual signs or symptoms. Only one AE per line should be recorded in the AE CRF; for example, an AE of nausea and vomiting would be listed as two separate events: the event of nausea and the event of vomiting. If a diagnosis is established after symptoms are recorded on the AE CRF, the diagnosis must be recorded, and the symptoms collapsed (removed; i.e., lined through and initialed). Whenever possible, abnormal laboratory results must be reported as their clinical corollary (e.g., low potassium should be recorded as hypokalemia).

A continuous AE with varying grades of severity must be recorded as one AE. The highest grade of severity experienced by that subject during the course of the continuous AE must be recorded.

Any condition noted before the subject signs the ICF will be listed as Medical History and is considered a pre-existing condition. If a pre-existing condition changes (i.e., becomes more severe or more frequent) at any time after the ICF is signed, or after study drug administration, it is considered an AE. Note: A change in treatment for a pre-existing condition (e.g., new high blood pressure medication), does not necessarily indicate an AE.

Information recorded on the AE CRF will include the AE term, the date and time of onset, severity, seriousness, relationship to study drug, action taken with subject due to AE, and the outcome of the AE, including the date and time of resolution, if applicable.

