9.8. Safety Assessments

Adverse events (AEs) and Serious AEs (SAEs) will be recorded from the time of informed consent through POD14.

Adverse events will be coded using the Medical Dictionary for Regulatory Activities (MedDRA version 23.1). The summary tables will be based on the Safety analysis set.

A treatment emergent adverse event (TEAE) is any adverse event with the onset date and time on or after the start date and time of study drug administration and ending with POD 14 ± 3 days.

All AE summaries will present TEAEs only; AEs that are not treatment-emergent will be included in listings but not summarized.

An overview of all TEAEs will present the number (and %) of unique subjects in the following categories:

- Any TEAE
 - Maximum severity: Mild
 - Maximum severity: Moderate
 - Maximum severity: Severe
- At least one related TEAE
- At least one serious TEAE
- Subjects discontinued due to a TEAE
- Died on study

Subjects will be counted once in each of the above categories.

The subject incidence of all TEAEs will be tabulated by the number (and %) of subjects reporting the TEAE. Incidence is defined as a subject reporting at least one TEAE within the summary level. Summary levels are 'at least one TEAE', System Organ Class (SOC) and Preferred Term (PT). Subjects will be counted only once within each reporting level in the table. For example if a subject reports a TEAE of headache on two separate occasions, the subject will be counted only once in the headache row of the table. Similarly if a subject reports two separate TEAEs within the same SOC the subject will only be counted once in the summary row for that SOC. For summary purpose, AE relationship to the study drug will be grouped into "Unrelated" for "unrelated" or "unlikely" and "Related" for "possible", "probable", or "definite". For subjects with more than one event coded to the same PT, the subjects will be counted for the categories with the strongest relationship and the greatest severity. A summary of subjects reporting at least one TEAE during the study will also be presented.

- TEAEs by PT (Preferred Term) sorted by the decreasing order of subject incidence in the group combining EXPAREL and EXPAREL admixed with 0.25% bupivacaine HCl
- TEAEs by SOC (System Organ Class) and PT sorted alphabetically
- TEAEs by SOC and PT, and worst severity
- TEAEs by SOC and PT and study drug-relationship
- TEAE of special interest (TEAESI) by SOC and PT

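### The closing safety call may be made from POD 11 although the safety endpoint runs through POD 14, and the SAP ends the treatment-emergent period in three different ways

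*Protocol*

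**What the plan says.** **Timing of the call.** Protocol section 9.2 states "A follow-up phone call will occur on Post-operative Day (POD) 14", and the sentence continues with a tolerance of 3 days before or after. The synopsis and Table 1 carry the same tolerance. Section 9.2 also says "No more than 30 days should pass between signing the ICF and study drug administration" and concludes that "each subject may participate in the study for up to a maximum of 47 days".

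**Period the safety data should cover.** Protocol section 12.4 defines the endpoint as "Incidence of treatment-emergent AEs and SAEs from the start of block procedure through POD 14". Section 14.1.2 requires that "all AEs that occur through POD 14 must be recorded regardless of whether or not they are considered related to study drug"; after POD 14 it requires only events the investigator judges related. Neither section mentions a tolerance.

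**Contacts after discharge.** Cohort 2 leaves the facility after the 96 h assessments and Cohort 1 after the 168 h assessments. Section 13.9 then lists only the daily worst and average pain scores. Section 13.10 provides for unscheduled visits if a sensory or motor deficit persists at POD 7. Section 13.11 contains the adverse event question: "Ask the subject about any new AE(s) and the resolution of any ongoing adverse event(s) since discharge".

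**SAP.** Section 5 defines a treatment-emergent event by its start only. Section 8.2 repeats the endpoint through POD 14. Section 9.8 requires onset "on or after the start date and time of study drug administration and ending with POD 14" and then adds plus or minus 3 days. It also says that all adverse event summaries show treatment-emergent events only, so this definition decides what enters the tables.

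**The concern.** A visit window placed evenly around the last day of an endpoint lets the last contact fall inside the period it is meant to close. A site can keep to the schedule and still not ask about the last days, and no second contact is planned for a subject called early. The events at issue include some that the protocol itself singles out: section 14.1.7 lists persistent tingling, numbness and weakness as being of special interest, and section 13.7 asks for at least 2 weeks without weight bearing to limit falls. POD 12 to 14 is thus part of the period the sponsor wants to know about.

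The SAP wording is a separate matter and would need attention even if every call were made on POD 14. A programmer given sections 5, 8.2 and 9.8 cannot tell on which day to stop counting. If the stop differs between subjects, one crude percentage pools unequal observation periods.

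**Working it through.** **1. Is the tolerance real on both sides?** Inputs from protocol section 9.2: 30 days from consent to dosing, call on POD 14, tolerance 3 days.

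- Maximum participation = 30 + 14 + 3 = 47 days, which reproduces the stated figure. Without the tolerance it would be 30 + 14 = 44. The plan does use the tolerance.
- Earliest call = 14 - 3 = POD 11. Latest call = 14 + 3 = POD 17.

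**2. Days with no scheduled adverse event question.** Count POD 0 to POD 14 as 15 calendar days and treat the day of the call as covered. Days left = max(0, 14 - call day).

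| Call on | Days left to POD 14 | Share of 15 days |
|---|---|---|
| POD 11 | 3 | 20.0% |
| POD 12 | 2 | 13.3% |
| POD 13 | 1 | 6.7% |
| POD 14 to 17 | 0 | 0% |

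On POD 1 to 14 alone, the worst case is 3/14 = 21.4%.

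**3. How many subjects and events?** The documents give neither the distribution of call days nor a late event rate, so these figures are illustrations resting on assumptions.

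- If calls were spread evenly over the 7 days POD 11 to 17, 3/7 = 43% of subjects would be called before POD 14. The mean shortfall would be (3 + 2 + 1)/7 = 0.86 days per subject.
- Assume a constant daily risk h of a first event. The chance of a first event on POD 12 to 14 is 1 - (1 - h)³. For h = 0.5%, 1% and 2% this is 1.5%, 3.0% and 5.9%. In an arm of 40 that is about 0.6, 1.2 and 2.4 subjects if all were called on POD 11 and none had an earlier event.
- With calls spread evenly, average 1 - (1 - h)^k over the seven call days (k = 3, 2, 1, then 0 four times) and multiply by 40. The result is about 0.2, 0.3 and 0.7 subjects per arm.

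These are upper figures for missed events, because some events would reach the site anyway.

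**4. The SAP definitions side by side.** Take an adverse event with onset on POD 16.

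- Section 5: treatment-emergent, because no end is given.
- Section 8.2: outside the endpoint, which stops at POD 14.
- Section 9.8, read as ending on the actual call day: counted only if the subject was called on POD 16 or 17. The period would end anywhere from POD 11 to POD 17, a spread of 6 days between subjects.
- Section 9.8, read as an outer limit of POD 17: counted for everyone. But under protocol section 14.1.2 an unrelated event on that day need not have been reported, so POD 15 to 17 would be collected under a narrower rule than POD 0 to 14.

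Neither reading of section 9.8 agrees with section 8.2.

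**The case against.** The best reply is that the call does not end adverse event collection. Section 14.1.2 binds the investigator to record every event through POD 14. Section 14.2.2 requires any serious event in that period to be reported within 24 hours of discovery. This stands. A reader might infer that POD 12 to 14 goes unobserved after an early call; the documents support only that those days lack a scheduled question.

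Two further inferences are tempting and should not be drawn.

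- *Late nerve deficits are lost.* Section 13.10 brings back a subject whose deficit persists at POD 7, through POD 14 or until recovery, with events and medication recorded. Those visits are at the investigator's discretion, and scheduled sensory and motor testing is in Cohort 1 only. The route is therefore partial cover, but it does not depend on the call.
- *Opioid results are damaged.* The total opioid endpoint closes at 96 h, before discharge. After discharge the e-diary is the main source (SAP section 9.2.1) and its daily assessments run to POD 14; the call asks only for medication not entered there. Time to first opioid is censored at End of Study, which is the ordinary handling of unequal follow-up.

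It can also be said that SAP section 5 is a general definition and that section 8.2 supplies the limit. That reading reconciles those two sections. It does not reconcile section 9.8. Nor is it established that subjects will be counted over 11 to 17 days: that is one of two readings of an unclear phrase.

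Finally, the window is identical in all arms, staff making the postsurgical assessments are blinded, and safety is only summarised descriptively. No mechanism for a difference between arms is apparent.

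**Conclusion.** The point holds as a minor one, in two parts. First, subjects called on POD 11 to 13 have 1 to 3 of 15 days of the stated safety period with no scheduled adverse event question. Second, the SAP's treatment-emergent period has three different ends, and the one in the analysis section is not a fixed day. The consequence is incomplete and uneven descriptive safety counts. The primary endpoint (0 to 96 h), the sample size and the efficacy comparisons are untouched.

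The day counts follow from the documents. The 43% and the per-arm event numbers depend on assumed call dates and event rates; POD 14 is the nominal target, so an even spread may well overstate early calls. That the call is the only scheduled adverse event question rests on the text of protocol sections 13.8 to 13.11; the lower rows of Table 1 could not be read in the copy available and should be checked against it.

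**What to change.** **Protocol.** Set the call to POD 14 with up to 3 days after and none before. Make the change wherever the tolerance appears: the synopsis, section 9.2, Table 1 and the SAP's copy of that schedule. Every completed call then covers POD 0 to 14, and the maximum stays 30 + 14 + 3 = 47 days.

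**SAP.** In sections 5 and 9.8 use one cut-off that matches section 8.2: tabulate adverse events with onset from the start of study drug administration through POD 14, and show later events in listings only.

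**Cost.** A few lines in two documents, and a calling window of 4 days (POD 14 to 17) instead of 7 (POD 11 to 17). SAP section 5 indicates that enrolment was already under way, so the new window can help only subjects not yet called. For the others, a count by arm of calls made before POD 14 would show how much was left unasked. The SAP correction applies to everyone, and should be made even if the sponsor keeps the call window.
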